[figure not shown]

Association between Vitamin D and The Development of Uterine Fibroids

2018.3.15

Study objectives The primary objective of this part is to assess the efficacy of supplementation with vitamin D on inhibiting the development of uterine fibroids in one year and two years. The secondary objective of this study is to evaluate the safety of supplementation with vitamin D in subjects.

Trial design This is an open-label, randomised controlled trial. After signing of informed consent, patients with vitamin D deficiency ($12 \text{ ng/ml} \leq \text{Serum 25-hydroxyvitamin D}_3 < 20 \text{ ng/ml}$) and uterine fibroids will be randomly assigned in a 1:1 ratio to intervention group A or control group B. Intervention group A will accept an oral dose of 1600 IU/day vitamin D₃ for up to 2 years. Control group B will receive 2 years follow-up. Patients with vitamin D insufficiency ($20 \text{ ng/ml} \leq \text{Serum 25-hydroxyvitamin D}_3 < 30 \text{ ng/ml}$) and uterine fibroids will be randomly assigned in a 1:1 ratio to intervention group C or control group D. Intervention group C will accept an oral dose of 800 IU/day vitamin D₃ for up to 2 years. Control group D will receive 2 years follow-up. Gynecologic ultrasound examinations will be performed every three months. The mount, location and size of the uterine fibroids will be documented (the transverse, longitudinal, and antero-posterior diameters of fibroids will be documented at each efficacy ultrasound examination for volume calculation). Percent change in volume of the total fibroids compared to baseline in different groups (baseline = last value obtained before randomization). Three perpendicular diameters (d₁, d₂, and d₃) were collected for each fibroid, and the volume of each fibroid (in cm³) was calculated with the ellipsoid formula: $4/3 * \pi * (d_1 * d_2 * d_3)/8$. For each patient, the total volume of fibroids (defined as the sum of the volumes of all the fibroids detected) was also calculated. The safety of vitamin D in subjects with uterine fibroids will be evaluated, including blood routine examination, electrolyte, hepatic and renal function, liver and urinary system ultrasound, and serum 25-hydroxyvitamin D₃. Vitamin D₃ Drops are purchased from Sinopharm star shark pharmaceutical (xiamen) co., LTD. An overview of the study design is shown in Figure 2 and Table 2.

[figure not shown]

Figure 2 flow diagram.

Table 2:time of date collection

Follow-up	1	2	3	4	5	6	7	8	9

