Months	0	3	6	9	12	15	18	21	24
The form of follow-up	Out-patient								
Informed consent	X								
Medical history	X								
Physical examination	X								
Serum 25-hydroxyvitamin D ₃	X	X	X	X	X	X	X	X	X
Urine pregnancy test	X	X	X	X	X	X	X	X	X
Gynecologic ultrasound	X	X	X	X	X	X	X	X	X
Hepatic and renal function	X		X		X		X		X
Electrolyte	X		X		X		X		X
Blood routine examination	X		X		X		X		X
Liver and urinary		X			X				X
System ultrasound			X						
Side-effect assessment		X	X	X	X	X	X	X	X
Changes in menstruation		X	X	X	X	X	X	X	X
Adverse event assessment		X	X	X	X	X	X	X	X
Vitamin D receptor genotype	X								

Sample size According to a previous study, the volume of uterine fibroids was 8.2 (2.1-30.5) cm³ after the supplement of vitamin D 12 months and 11.4 (5.5-22.3) cm³ in the control group, respectively. On the basis of a 0.9 power to detect a significant difference ($\alpha=0.05$, one-sided), 320 participants will be required for the four groups and in a 1:1:1:1 ratio. Allowing for a 10% withdrawal rate, we plan to include 360 patients in the whole trial.

Inclusion criteria

1. Patients are willing to cooperate with the follow-up and sign informed consent;
2. Females aged 35-50 who are diagnosed as having uterine fibroids by transvaginal or abdominal ultrasonography;
3. The maximum average diameter of intramural myoma is $\leq 4\text{cm}$, $\geq 1\text{cm}$; The amount of myoma is less than 4;
4. Serum 25-hydroxyvitamin D₃ $< 30\text{ ng/ml}$, $\geq 12\text{ ng/ml}$.

Exclusion criteria

1. Patients with heavy menstrual bleeding ($>80.0\text{ mL}$), menstrual disorders, pelvic discomfort, infertility, or other indications for operation;

2. Patients complicated with myoma degeneration and adenomyosis that were suspected or diagnosed by ultrasound or gynecologic examination;
3. Allergic to vitamin D₃;
4. Use of sexual hormone, mifepristone, gonadotropin-releasing hormone agonist (GnRHa), or other medication which is likely to interfere with uterine fibroids within 3 months;
5. Pregnancy, lactation, postmenopause, or planned pregnancy within two years;
6. Suspected or identified as other tumors of genital tract;
7. History of osteoporosis or vitamin D deficiency taking vitamin D supplements within previous one month;
8. History of autoimmune diseases, infectious diseases (tuberculosis, AIDS), autoimmune diseases, digestive system diseases (malabsorption, crohn disease, and dysentery);

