9. Alanine aminotransferase (ALT) or aspartate transaminase (AST) more than 3 times of the normal upper limit, total bilirubin (TBIL) more than 2 times of the normal upper limit;
10. Creatinine levels ≥ 1.4 mg/dL (123 μ mol/L) or creatinine clearance ≤ 50 mL/min;
11. History of malignant tumors;
12. Simultaneous participation in another clinical study with investigational medicinal product(s) or researcher thinks the subjects are not suitable for this trial.

Outcomes measures Primary outcomes: percent change in volume of the largest fibroid and total fibroids compared to baseline (baseline = last value obtained before randomization; measured by ultrasound examination). Secondary outcomes: percentage of subjects undergoing other medical or surgical treatment, hypercalcemia, urinary calculus, abnormal liver and renal function. Ultrasound examinations will be performed by a physician well experienced in gynecology. If possible, the same examiner should conduct all examinations of a subject throughout the study and the same ultrasound machine (per site) should be used throughout the study. For each subject, the most appropriate ultrasound method (transvaginal or abdominal) should be used depending on fibroids location and this method should be used consistently throughout the study.

Withdrawal Subjects must be withdrawn from the study when one of the following criteria occurs:

1. At their own request. At any time during the study and without giving reasons, a subject may decline to participate further. The subject will not suffer any disadvantages as a result;
2. In the investigator's opinion, continuation of the study treatment would be harmful to the subject's health;
3. Obvious non-compliance;
4. Lost to follow-up;
5. Pregnancy;
6. Other medical or surgical treatments of uterine fibroids.
7. Receive other medical treatments which may affect the level of serum 25-hydroxyvitamin D₃ or other surgical treatments.

8. The level of serum calcium > 3.5 mmol/L or serum 25-hydroxyvitamin D₃ > 100 ng/mL.

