Safety assessments Safety will be assessed by renal and liver function test, electrolyte, routine blood test, and serum 25-hydroxyvitamin D₃. Urine pregnancy test and serum 25-hydroxyvitamin D₃ level will be detected every three months. Other indicators are detected during the period of screening and after the treatment of every six months. Liver and urinary system ultrasound will be conducted after the treatment of 12 months and 24 months. The occurrence of any adverse events in trial participants will be recorded in the case report forms during each patient visit. We will withdraw patients who have severe adverse events, as it is unsafe for them to continue the trial. Meanwhile, we will give them relevant medical care and follow them up until the reaction has terminated.

Statistical analysis Statistical analyses will be performed using SPSS version 22.0 for Windows (SPSS Inc., Chicago, IL, USA). The randomisation sequence is generated by the use of the SPSS software. The normality of distribution of continuous variables are tested by one-sample Kolmogorov-Smirnov test. Continuous variables with normal distribution are reported as mean (standard deviation); non-normal variables are presented as median (interquartile range). Means of 2 and 3 or more continuous normally distributed variables, respectively, are compared by independent samples Student's t test or one-way ANOVA test. Mann-Whitney U test and Kruskal-Wallis test are used, respectively, to compare means of 2 and 3 or more groups of variables not normally distributed. The frequencies of categorical variables are compared using Pearson χ^2 or Fisher's exact test, when appropriate. A value of $P < 0.05$ is considered significant.

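### Within each randomised comparison, two unranked primary volumes and two time points share one flat 5% threshold, and no success rule says which result decides

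*Combined protocol and SAP*

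**What the plan says.** - **Contrasts.** Under Trial design, women with deficiency and "uterine fibroids will be randomly assigned in a 1:1 ratio to intervention group A or control group B"; women with insufficiency and "uterine fibroids will be randomly assigned in a 1:1 ratio to intervention group C or control group D". These are two separate randomisations.
- **Time points.** Study objectives gives the primary aim as "to assess the efficacy of supplementation with vitamin D on inhibiting the development of uterine fibroids in one year and two years". Neither year is put first.
- **Primary outcomes.** Outcomes measures lists "percent change in volume of the largest fibroid and total fibroids compared to baseline". It does not rank the two volumes, attach a visit to them, or say whether one or both must succeed.
- **A partial lead.** Trial design describes the group comparison for one volume only: "Percent change in volume of the total fibroids compared to baseline in different groups". This favours total volume but does not make it the sole primary outcome.
- **Tests.** Statistical analysis chooses by distribution: t test or Mann-Whitney for two groups, ANOVA or Kruskal-Wallis for three or more. It does not say which of these is primary for the volumes, and it closes with "A value of $P < 0.05$ is considered significant".
- **Sidedness.** Sample size uses alpha 0.05 one-sided, with volumes measured "after the supplement of vitamin D 12 months". The analysis section does not mention sidedness.

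**The concern.** Each randomised comparison yields four primary results (two volumes by two years), and each can be held against the same threshold. Two careful readers could apply this plan to the same data and disagree. One might claim benefit from the largest fibroid at 24 months alone; the other might require all four results. If the rule is settled after the data are seen, the chance of a false claim of benefit depends on which rule is picked. The trial is open-label, which makes it more important to fix the rule beforehand.

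Two smaller gaps compound this. A four-group ANOVA or Kruskal-Wallis test would mix women from different vitamin D strata and would isolate neither randomised contrast. And a two-sided analysis of a trial sized one-sided would have less power than the plan states.

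**Working it through.** **Plan's own figures.** 320 / 4 = 80 per arm. With 10% withdrawal, 320 / 0.9 = 356, close to the stated 360. The 320 does not follow from the quoted volumes under standard readings. That is a separate matter, so 80 per arm at 90% power is taken here at face value.

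**False claims within one comparison.** With no treatment effect, treat the four results as standard normal statistics. The correlation is r_v between the two volumes in the same year, r_t between years for the same volume, and r_v × r_t otherwise. A result counts when z > 1.645 (one-sided 0.05) or z > 1.960 (benefit side of two-sided 0.05). High values of r_v are plausible because total volume is "defined as the sum of the volumes of all the fibroids detected", so it includes the largest fibroid. The documents give no correlations, so all values below are assumed. Rates come from 2,000,000 simulated draws, shown as one-sided 0.05 / two-sided 0.05.

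| r_v / r_t | Any one of four | Total volume, either year | Both volumes, either year | All four |
|---|---|---|---|---|
| 0.80 / 0.5 | 13.0% / 7.0% | 8.8% / 4.5% | 4.5% / 2.1% | 0.5% / 0.1% |
| 0.90 / 0.5 | 11.8% / 6.3% | 8.8% / 4.5% | 5.7% / 2.7% | 0.6% / 0.2% |
| 0.95 / 0.7 | 10.0% / 5.3% | 8.0% / 4.2% | 6.1% / 3.0% | 1.3% / 0.5% |
| 0.98 / 0.9 | 7.9% / 4.1% | 6.8% / 3.5% | 5.8% / 2.9% | 2.6% / 1.2% |

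Nominal is 5% / 2.5%. For the any-one rule, 7.9 / 5 = 1.6 and 7.0 / 2.5 = 2.8, so the rate is 1.6 to 2.8 times nominal. The same model at the other two corners of the assumed range (0.80 / 0.9 and 0.98 / 0.5) gives 10.1% one-sided for any one of four, inside that span. For both volumes in either year those corners give 3.5% and 7.4%, so that rule falls on either side of nominal depending on the correlation. For reference, four independent tests would give 1 − 0.95⁴ = 18.5%.

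**Across the two comparisons.** The strata are independent, so a rate p in each becomes 1 − (1 − p)². One test per stratum at full alpha gives 1 − 0.95² = 9.75%, or 1 − 0.975² = 4.9%. This matters only if a win in either stratum would support a single trial-wide claim.

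**Sidedness and power.** Power of 90% at one-sided 0.05 means an expected z of 1.645 + 1.282 = 2.926 (from unrounded quantiles).
- At one-sided 0.025 (two-sided 0.05): Φ(2.926 − 1.960) = Φ(0.966) = 83%.
- At one-sided 0.0125: Φ(2.926 − 2.241) = Φ(0.685) = 75%.
- Keeping 90% at two-sided 0.05: 80 × (3.242 / 2.926)² = 98.2, so 99 per arm.

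The noncentral t distribution gives 83.2% and 75.0% for the first two.

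**The case against.** The best defence is that the plan says more than it may seem to. Randomisation fixes the natural contrasts, and the analysis section does select a two-group test by distribution. The sample size does state one-sided 0.05. Both the objective and the outcome definition join their parts with *and*, which can be read as requiring everything; on that reading the error rate is below nominal. All of this stands, and it rules out three stronger readings that a reader might infer.

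- *That the plan names no test and no sidedness.* It does name them. What is missing is the statement that the two-group contrasts are primary and that the one-sided level applies to the analysis.
- *That the plan inflates the error rate as written.* It adopts no any-one rule. It also adopts no all-four rule, and nothing in it prevents a claim from a single result.
- *That the whole trial carries the error of eight independent tests (1 − 0.95⁸ = 33.7%).* The volumes come from the same scans and overlap, so they are not independent. The strata are separate populations, randomised separately, and no passage makes a pooled claim. Full alpha for each is defensible.

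Two limits also apply to the table. Its rates rest on assumed correlations. They are not upper bounds either, because Table 2 schedules eight post-baseline ultrasounds and the outcome definition does not restrict which of them is analysed.

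**Conclusion.** The point holds as a gap in the decision rule. For each of A vs B and C vs D, the plan does not say which volume, which year or which combination decides, and it applies one unadjusted 5% threshold.

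- Any one of four counts: about 8-13% false claims of benefit per comparison one-sided, or 4-7% in the benefit direction two-sided (1.6 to 2.8 times nominal).
- All four required: at most about 2.6% / 1.2%, so no inflation.
- Both volumes in either year: around nominal, with the direction set by the correlation.

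These figures assume correlations of 0.8-0.98 between volumes and 0.5-0.9 between years. Separately, analysing at two-sided 0.05 would lower the plan's own 90% power to about 83%, taking 80 per arm at face value. This is a cheap improvement; it does not show that the design is invalid.

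**What to change.** Add one paragraph to Statistical analysis before outcome data are examined:

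1. Use the same sidedness in the sample size and the analysis. If it becomes two-sided, restate the power.
2. Make A vs B and C vs D the primary contrasts, and say that four-group tests are not primary.
3. Within each contrast, name one primary volume and visit. Total fibroid volume at 12 months is one reasonable choice, since Trial design describes that volume and the sample size uses that visit. Test the other volume-by-year results in a pre-stated fixed sequence at the same alpha, which holds the rate per contrast at nominal. If both years are to stay equal, as the objective lists them, share alpha between them or require both.
4. State that the two strata are separate questions, each at full alpha. If one trial-wide claim will be made, split alpha between them: 1 − 0.975² = 4.9% one-sided.

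**Cost.** No new data are needed. Isolated nominal results could no longer be called positive. With a 12-month gate, a benefit seen only at 24 months could rarely be claimed, because the gate would open only by chance, at about the alpha level; the sponsor should weigh this against the equal-years options. Splitting alpha between strata lowers power per stratum from 90% to about 83% one-sided, or from 83% to 75% two-sided. Sharing alpha equally between years has the same cost for each year's test. Requiring both years costs no alpha, but power cannot exceed that of the weaker year.
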